5. ESRD
6. CR or PR, and CR alone at 6, 12, 18, and 24 months after randomization
7. Time to CR or PR
8. Effect of treatment on renal function, as assessed by slope of creatinine clearance from baseline to 24 months.

Table 1. Definition of remission status

Remission status	Proteinuria (UP g/24 hours) after treatment
Complete remission (CR)	UP \leq 0.3 g/24h and serum albumin \geq 3.5g/dl
Partial remission (PR)	Reduction in baseline UP of \geq 50% plus final UP \leq 3.5 g/24h but $>$ 0.3 g/24h
Non-response (NR)	Reduction in baseline UP of $<$ 25% (includes increase in UP)
Relapse	Development of nephrotic range proteinuria following CR or PR, i.e. $>$ 3.5g/24h

Patient recruitment

The study population will be comprised of individuals with biopsy-proven idiopathic MN. Total study size will be 126 patients, enrolled among up to 25 participating sites. Potential candidates for the study will be identified by the investigators using existing databases and clinical trial networks. The P.I. or the study coordinator will contact these potential candidates and if the preliminary interview indicates their willingness to participate, a consent form will be reviewed with the patient. If a potential candidate remains interested, the consent form will be signed, and the patient enrolled in the study. The institutional review board at each participating site will approve the recruitment process and consent forms. The Mayo Nephrology Collaborative Group (MNCG) will post information on its web site describing the study and identifying local contacts at the collaborating centers. Each site involved may have their own methods of informing and recruiting potentially eligible patients but in all cases will have IRB approval before embarking on this process. Each site will be expected to randomize approximately 6-10 patients over the recruitment period. If, based on site estimates of the IMN population that would be eligible for this study, we enroll approximately 30% of the annual population in a single year our recruitment will be complete. We have assembled a consortium for this trial with a population that well exceeds the enrollment needs based upon the multi-year enrollment plan for this trial.

Recruitment strategy

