- Estimated GFR $\geq 40 \text{ ml/min}/1.73\text{m}^2$ while taking ACEi/ARB therapy OR quantified endogenous creatinine clearance $\geq 40 \text{ ml/min}$ based on a 24 hour urine collection. The GFR will be estimated using the 4 variable MDRD equation as published in the NKF-CKD guidelines.⁸¹ This approach is adopted, rather than the much more expensive and more invasive techniques (e.g. inulin or iothalamate clearance) since the likelihood of detecting significant changes in GFR in this short term study is remote regardless of which method is chosen. At entry into the study and at set time points thereafter patients will also have a 24h urine collection for calculation of CrCl and proteinuria.

Exclusion Criteria

- Patients with presence of active infection or a secondary cause of IMN (e.g. hepatitis B, SLE, medications, malignancies). Testing for HIV, Hepatitis B and C should have occurred < 2 years prior to enrollment into the study. Screening for malignancy should be carried out according to standard guideline recommendations.
- Type 1 or 2 diabetes mellitus: to exclude proteinuria secondary to diabetic nephropathy. Patients who have recent history of steroid induced diabetes but no evidence on renal biopsy performed within 6 months of entry into the study are eligible for enrollment.
- Pregnancy or breast feeding (for safety reasons).
- History of resistance to CSA (or other calcineurin inhibitors, e.g. tacrolimus), RTX or alkylating agents (e.g. Cytoxan). Patients who previously responded to CSA/CNI, RTX or alkylating agents with either a CR or PR but relapsed off CSA/CNI after 3 months, or relapsed off RTX or alkylating agent after 6 months, are eligible.

Randomized Treatment Groups: Once all entry criteria have been satisfied and confirmed, patients will be randomized to treatment with Rituximab or Cyclosporine. Randomization will be performed by study site staff through the electronic case report form (eCRF.) The randomization list will be stratified by site, and generated by the Data Management and Coordinating Center (DMCC) using random permuted blocks of variable size.

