
Statistical and Analytical Plan: All demographics and entry laboratory data will be summarized by treatment group. Frequency distributions will be used to describe categorical values and basic summary statistics (mean, standard deviation, median, and inter-quartile range) will be used to describe continuous values. To provide more reliable estimates and minimize the “regression to the mean effect” duplicate urine measurements obtained at baseline (Time 0), 6, 12, 18 and 24 months will be averaged. The chi-square test and logistic regression will also be used to compare the percent of patients with remission at 6, 12, 18, and 24 months adjusting for treatment center and the baseline

proteinuria (UP<8g/24h vs >=8g/24h). Odds ratios and associated 95% confidence intervals will be estimated. The formal test for the primary endpoint will be based on the significance of the treatment group factor in the logistic regression model for UP failure at month 24. The Wilcoxon rank-sum test and ordinal logistic regression will be used to compare the ordered remission status outcome (1=CR, 2=PR, 3=NR) between treatment groups. Longitudinal methods for categorical outcomes (e.g. generalized estimating equation or GEE models) will be used to compare remission status profiles between treatment arms. Unless otherwise noted, all tests will be two-sided with alpha level 0.05.

For repeated measures such as urine protein, individual rates of change will be estimated using within-patient linear regression analyses (including data from all visits). Because of the non-linearity of the changes in proteinuria log transformation estimates will be used. Renal function readings will be censored at initiation of dialysis or renal transplant. Additionally, mixed effects models, assuming a random center effect, and a random slope of creatinine clearance and/or reciprocal of creatinine and intercept for each patient will be fit using data from all visits. These models allow comparison of the average slope between groups, while taking into account that each patient's slope may be based on a variable number of readings. Treatment group comparisons regarding quality-of-life scales will be done using repeated measures analyses and mixed effects models.

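### The primary logistic model adjusts for centre without saying how; entered as site indicators, centre miscalibrates the treatment test and exaggerates the odds ratio

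*Combined protocol and SAP*

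**What the plan says.** Under Statistical and Analytical Plan, remission at months 6, 12, 18 and 24 is compared by chi-square and by logistic regression "adjusting for treatment center and the baseline" value "proteinuria (UP<8g/24h vs >=8g/24h"). Odds ratios with 95% confidence intervals are promised. On the primary endpoint the section states: "The formal test for the primary endpoint will be based on the significance of the treatment group factor in the logistic regression model" at month 24. Tests are two-sided at 0.05 unless otherwise noted.

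The same section specifies "mixed effects models, assuming a random center effect" for the creatinine slope analyses. No such wording accompanies the logistic model. It has no rule for pooling small sites and names no conditional or stratified alternative.

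Patient recruitment gives the scale: "Total study size will be 126 patients, enrolled among up to 25 participating sites", and "Each site will be expected to randomize approximately 6-10 patients over the recruitment period". Under Randomized Treatment Groups, "The randomization list will be stratified by site", with permuted blocks of variable size.

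Under Sample size estimation, the hypothesis is non-inferiority within 15 percentage points, with 55% versus 45% assumed, one-sided alpha 0.025 and 63 patients per arm.

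**The concern.** Adjusting for centre is reasonable when randomization is stratified by site. The difficulty is the method. Since a random centre effect is named for one model and not for the other, an analyst would most naturally put centre into the logistic model as indicators. At 25 sites that means 24 nuisance parameters for 126 binary outcomes. Unconditional maximum likelihood behaves badly with many small strata: the log odds ratio is pushed away from zero when there is an effect, the standard error is too small, and a site where every patient has the same outcome carries no information.

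At stake are the calibration of the test that the plan calls its formal primary test, any superiority statement built on it, and the odds ratios and intervals reported at all four visits.

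**Working it through.** **1. The plan's own figure.** With unpooled variance, n per arm = (1.960 + 0.842)² × (0.45×0.55 + 0.55×0.45) / (0.10 + 0.15)² = 7.85 × 0.495 / 0.0625 = 62.2, so 63. Power at 63 is 80.5%. The stated sample size reproduces, with almost no headroom.

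**2. Patients per site.** At the maximum, 126/25 = 5.04. At the expected 6-10 per site, 126/6 = 21 sites and 126/10 = 12.6, so about 13 to 21 sites.

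**3. Simulation inputs.** From the documents: 126 patients, 1:1 allocation stratified by site, binary baseline proteinuria, response 45% on CSA and 55% on RTX, margin 15 points. Assumed: blocks of 2 and 4; 60% of patients at or above 8 g/24h; log OR -0.7 for that class; centre SD 0.3 on the logit scale (0 and 0.5 also run).

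The margin on the log-odds scale uses 45% versus 30%: OR = (0.30/0.70)/(0.45/0.55) = 0.524, log OR -0.647. There were 6000 runs with no effect and at the margin, and 3000 at 55% versus 45%. Tests are Wald tests.

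**4. Results (site indicators, then comparators).**

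| Sites × patients | Estimated / true log OR, 45% vs 30% | Two-sided type I error: indicators / no centre / conditional / Mantel-Haenszel | False non-inferiority: indicators / no centre | Non-inferiority power: indicators / no centre |
|---|---|---|---|---|
| 25 × 5 | 1.30 | 7.4 / 4.3 / 4.8 / 4.8% | 1.9 / 2.5% | 75.9 / 81.9% |
| 21 × 6 | 1.25 | 7.0 / 4.7 / 4.4 / 4.7% | 1.7 / 2.4% | 77.8 / 82.3% |
| 16 × 8 | 1.19 | 6.5 / 4.9 / 4.9 / 4.9% | 2.2 / 2.6% | 77.2 / 80.9% |
| 13 × 10 | 1.13 | 6.6 / 4.9 / 5.0 / 5.3% | 2.3 / 2.6% | 79.1 / 81.5% |

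Monte Carlo standard error is about 0.3 points for the 5% rates and 0.2 for the 2.5% rates. At 55% versus 45% the log OR ratios are similar: 1.31, 1.26, 1.17 and 1.15. Across other centre SDs and unequal site sizes, type I error at 25 sites was 6.9-8.4%. A random-intercept model at 25 sites gave 4.8-5.1%.

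**5. Source of the excess error.** With no effect the estimate is centred at zero. The mean model standard error is 0.43, but the estimates vary with SD 0.49. The test is liberal because its standard error is too small; the estimate is not shifted.

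**6. Why power falls.** Without centre terms the standard error is about √[2/(63×0.45×0.55)] = 0.36. At 55% versus 45% the true log OR is 0.401, so the distance to the margin is (0.401 + 0.647)/0.36 = 2.9 standard errors. With indicators at 25 sites the mean estimate rises to 0.526, but the standard error is about 0.43: (0.526 + 0.647)/0.43 = 2.7. The larger standard error outweighs the larger estimate.

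**7. Sites that contribute nothing.** At 45% response in both arms and no centre variation, the expected number of patients in single-outcome sites of size m is 126 × (0.45^m + 0.55^m): 8.7 for m = 5, 4.5 for m = 6, 1.3 for m = 8. With 25 sites the simulated range was about 8-18 patients.

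**8. Check on the proposed risk difference.** The Mantel-Haenszel risk-difference interval had 79-80% non-inferiority power. It passed in 2.8-3.1% of runs at the simulated margin, but there the mean difference was -0.141 to -0.144, just inside -0.15. At -0.143, with standard error √[(0.2475 + 0.21)/63] = 0.085, the expected pass rate is 1 - Φ(1.96 - 0.007/0.085) = 3.0%. So this is not evidence of inflation.

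**The case against.** The plan never says that centre is a fixed covariate. That stands: the defect is an unspecified method whose most natural reading is a poor one, not a mandated wrong model.

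Five patients per site is the extreme. That stands too: the protocol expects 6-10, where the distortion is smaller but still present. One smaller run at 16 sites with centre SD 0.5 (2000 runs) gave a type I error of only 5.7%, with a Monte Carlo standard error of 0.5 points. Single-outcome sites are also a minor matter at 8 or more per site.

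A reader might infer that an exaggerated odds ratio favours the non-inferiority claim when RTX looks better. It does not. At the margin the true effect is unfavourable to RTX, so exaggeration moves the estimate further in the unfavourable direction; false non-inferiority is 1.7-2.3% against 2.5%. Where RTX is better, the larger standard error outweighs the larger estimate. The run at centre SD 0.5 agrees: false non-inferiority was 2.0% at 25 sites and 2.6% at 16, against 2.8% and 3.3% without centre, and power was 71% and 76% against 79% and 80%.

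Finally, if the primary decision were moved to a risk-difference interval, the odds-ratio bias would no longer touch it. That is correct, but the plan as written rests the formal test on the logistic treatment factor.

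**Conclusion.** The point holds as a gap in specification with a measurable cost. If centre is entered as site indicators, the treatment-factor test runs at about 6-7% at the expected site sizes and up to about 8% at 25 sites. Odds ratios for a real effect are exaggerated (log OR by about 13% to 25%, or 30% at 5 per site), and their intervals are too narrow. For non-inferiority on the log-odds scale, error is not inflated. The harm is lost power against a model without centre terms: 2.4 to 6.0 points at centre SD 0.3, and 4 to 8 points in the smaller SD 0.5 run.

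The sizes rest on the assumed block sizes, a centre SD of 0-0.5 and the assumed baseline covariate effect. The direction was the same in all settings tried. This is a worthwhile, cheap improvement; it does not undermine the design.

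**What to change.** State in the Statistical and Analytical Plan how centre enters the primary analysis, and that it does not enter as unpenalised site indicators. Any of these would do:

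- A site-stratified Mantel-Haenszel risk difference, with a rule fixed in advance for pooling small sites. This respects the stratified randomization and puts the confidence interval on the scale of the 15-point margin.
- A logistic model with a random centre intercept, as already planned for the creatinine slopes.
- Conditional logistic regression stratified by site.

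Apply the same choice to the remission comparisons at months 6, 12 and 18.

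The cost is one sentence, written before outcome data are examined by arm. The first option needs a pooling rule, and the second a distributional assumption for centre. The third still draws nothing from sites where all outcomes agree, but its test stays near 5%.

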Sample size estimation: The primary study goal is to compare the long-term efficacy of RTX (given at baseline and repeated at 6 months) with CSA (12 months treatment + 2 months taper) using proteinuria response 24 months after randomization. Proteinuria positive response will be defined as attaining and maintaining CR or PR at 24 months after randomization. We propose to establish that the RTX treatment is non-inferior to the CSA. RTX will be considered non-inferior to CSA if the response rate of the RTX arm is at most 15% worse than that of CSA arm. In addition we will compare the quality of life (QOL) and adverse event (AE) profile over the course of the treatment period. The preliminary data has indicated that CSA is effective in inducing a CR/PR of proteinuria in between 60 and 75% of MN cases.^{48, 51} However, nephrotic syndrome (NS) relapses may be as high as 50% once CSA is discontinued.⁸⁵ Thus, we estimate a CR/PR rate in patients treated with CSA of 30-50% at 24 months after randomization.⁸⁵ Similar remission and relapse rates with the use of Tacrolimus (another calcineurin inhibitor) have been reported by Praga et al.⁵⁶ In this latter study, almost half of the MN patients had a relapse of the nephrotic syndrome after tacrolimus was discontinued.⁵⁶ On the other hand, based on the long term follow up on the 35 patients treated with RTX from our 2 studies, we estimate the relapse rate to be <10% at 24 months.^{71, 75} We observed a CR/PR rate at 12 months, very similar to the rate for calcineurin inhibitors i.e. 60%, and in our second study completed recently, we observed an 80% CR/PR rate at 24 months, implying that RTX had a ~20% failure rate with 95% (CI 6% to 44%). To be conservative for the sample size estimation, we considered a maintained CR/PR rate at the low end of our previous experience, 55% CR/PR for RTX at 24 months and at the high end of our experience with CSA (CNI therapy) CR/PR for CSA of 45%. We propose a non-inferiority trial with non-inferiority margin $\delta = 15\%$, with the null hypothesis of $\pi_{RTX} - \pi_{cyclosporine} < \delta$, where π_{RTX} and $\pi_{cyclosporine}$ are the proportions of patients with CR/PR at 24 months in treatment arms of RTX and CSA, respectively. Under these assumptions, and a one sided alpha of 0.025, enrollment of 63 evaluable patients per study arm is required to achieve 80% power to show that the RTX is not inferior. For the intent to treat (ITT) analysis we will consider all patients lost to follow up to be non-responders so no correction to the sample size is needed for dropouts. With 63 patients per arm we will have 80% power to detect moderate differences of .6 standard deviations for continuous measures or around .25 for proportions for the comparisons of the QOL and AEs.

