Adverse events (both patient and event counts) will be tabulated by body system, severity and, for each severity, by investigator-assessed relationship to study drug. Group comparisons for adverse events with 4 or more occurrences will be done using chi-square or Fisher's exact test. The last RTX injection is at 6 months and the tapering of Cyclosporine will be completed by the end of month 14. Hence, the adverse events analyses will focus on events through month 18, allowing these additional months for potential lingering Cyclosporine or RTX complications.

The analysis of the primary endpoint (urine protein failure at month 24) will be intent-to-treat (ITT), and will include all randomized subjects in the analysis. For those without a 24 month visit, the 18 month visit results will be used if available, otherwise they will be assumed to have failed at 24 months. Per protocol (PP) analyses will also be done including only those subjects who receive a full course of study medication and who have a 24 month visit.

Interim analyses: No interim analyses for efficacy will be performed during the trial, however safety data will be compiled and reviewed approximately every six months or at the request of the Data and Safety Monitoring Board.

Investigator and Coordinator Training: In order to make efficient use of funding, annual investigator and coordinator meetings will be coordinated with national nephrology meetings where possible. It is expected that the majority of the training will occur through web-based technology and will be coordinated through the data management and coordinating Center.

The **Data Management and Coordinating Center (DMCC)** is located at the Applied Health Research Center (AHRC) at St. Michael's Hospital/University of Toronto. The DMCC will be responsible for facilitating all aspects of the study planning, training, implementation, data collection and analysis.

The clinical information collected for this study will be stored at the DMCC at the Applied Health Research Centre of St. Michael's Hospital in Toronto, ON, Canada and also sent to a federal data repository held by the Office of Rare Diseases Research (ORDR) and located at the University of South Florida (USF) in Tampa, FL.

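### The formal primary test is a logistic test of no treatment difference, so the 15-point non-inferiority margin is never tested

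*Combined protocol and SAP*

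**What the plan says.** The Overview gives the study hypothesis and first specific aim as non-inferiority of RTX to CSA for long-term remission. Under Statistical Methods and Analysis, the sample size paragraph gives the criterion: RTX is non-inferior if "the response rate of the RTX arm is at most 15% worse than that of CSA arm". It works on the difference between two proportions at one-sided alpha 0.025, assumes 55% remission on RTX and 45% on CSA, and concludes that "enrollment of 63 evaluable patients per study arm is required to achieve 80% power to show that the RTX is not inferior".

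The Statistical and Analytical Plan that follows names the primary test: "The formal test for the primary endpoint will be based on the significance of the treatment group factor in the logistic regression model" for urine protein failure at month 24. The logistic model adjusts for treatment centre and baseline proteinuria. On effect estimates for remission it says: "Odds ratios and associated 95% confidence intervals will be estimated". The default error rate is: "Unless otherwise noted, all tests will be two-sided with alpha level 0.05".

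The primary analysis is then set as intention to treat, with a rule for missing month-24 visits and a supporting set: "Per protocol (PP) analyses will also be done including only those subjects who receive a full course of study medication" and who have a month-24 visit. The margin does not appear in the Statistical and Analytical Plan, in the definition of the analysis populations, or in any analysis described elsewhere in the document.

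**The concern.** The significance of a treatment factor in a logistic model ordinarily means a test of log odds ratio = 0, and the plan gives no shifted null. Running it one-sided at 0.025 instead of two-sided at 0.05 does not help, because there is still no margin in it.

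The planned odds-ratio interval does not close the gap either. The criterion is on the risk-difference scale, and no rule is given for moving from one scale to the other.

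A trial that clears the 15-point bound and a trial that fails it can therefore both be reported as not significant. The stated 80% power does not describe the test called formal. The margin-based estimate, its adjustment and its interval method would have to be settled later, in an open-label phase III trial, possibly with the data in hand.

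**Working it through.** **Inputs, all from the sample size paragraph.** RTX 0.55; CSA 0.45; margin 0.15 on the risk difference; one-sided alpha 0.025; 63 per arm; planning range for CSA 30–50%.

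**1. Reproduce the plan's sample size.** The variance term is 0.55×0.45 + 0.45×0.55 = 0.495. The distance from the margin is 0.10 + 0.15 = 0.25.

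n = (1.960 + 0.842)² × 0.495 / 0.25² = 62.2, so 63 per arm.

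The stated figure is reproduced, as the size of a margin-based test.

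**2. Power of each test with 63 per arm at 55% v 45%.** The standard error of the difference is √(0.495/63) = 0.0886.
- Margin-based: Φ(0.25/0.0886 − 1.960) = Φ(0.86) = 80.5%.
- Test of no difference: Φ(0.10/0.0886 − 1.960) = Φ(−0.83), about 20%.

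Exact binomial enumeration of all outcomes with 63 per arm, unadjusted, gives:

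| Quantity at 55% v 45% | Result |
|---|---|
| 95% CI lower limit above −15 points | 80.5% |
| OR = 1 rejected, chi-square | 22.0% |
| OR = 1 rejected, logistic Wald | 18.7% |
| Non-inferiority met, named test not significant for RTX | 58.6% (chi-square), 61.9% (Wald) |

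For scale, 80% power for the named test at these rates would need (1.960 + 0.842)² × 0.495 / 0.10², about 389 per arm (392 with pooled variance).

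**3. Two possible results with the same formal verdict.**
- 34/63 RTX v 28/63 CSA: difference +9.5 points, 95% CI −7.9 to +26.9; p = 0.29. The lower limit is above −15, so the criterion is met.
- 24/63 RTX v 28/63 CSA: difference −6.3 points, 95% CI −23.5 to +10.8; p = 0.47. The lower limit is below −15, so it is not met.

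The named test calls both not significant.

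**4. The margin is not one odds ratio.** A 15-point deficit gives a response odds ratio of [(p − 0.15)/(1 − p + 0.15)] / [p/(1 − p)], where p is the CSA rate.

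| CSA rate | Response OR at the margin | Failure OR (the modelled outcome) |
|---|---|---|
| 30% | 0.41 | 2.43 |
| 45% | 0.52 | 1.91 |
| 50% | 0.54 | 1.86 |

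A lower confidence limit of 0.45 for the response odds ratio would clear the margin at a CSA rate of 30% and miss it at 45%, both within the planning range.

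**5. A conditional figure.** The plan does not say that a non-significant result would be read as non-inferiority. If it were, a true 15-point deficit (30% v 45%) would pass 57.4% of the time by chi-square or 57.9% by logistic Wald, against 2.5% for the margin-based test.

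**The case against.** The strongest reply is that the sample size paragraph already fixes the margin, the scale, the direction in words and the one-sided alpha, and that the analysis text fixes the populations and the missing-data rule. On that view a competent analyst would apply the criterion, and only the estimator is open. This is partly right: the open choices are the adjustment and the interval method, not the margin. The unadjusted interval method hardly matters (80.5% power by Wald or Farrington–Manning, 80.6% by Newcombe). But the plan is not merely silent. It designates a different test as the formal one, and the two statements conflict.

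Second, the named test is not always uninformative. In the enumeration, no table with 63 per arm was significant for RTX yet failed the −15-point bound. That stands, and the criticism is limited to results not significant for RTX.

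Third, the power gap is a design-case figure. The plan calls 55% v 45% conservative. At 60% v 40% the named test has 60–64% power and the discordance falls to 34–38%; at 80% v 50% these are about 95% and 5%. At 60% v 50% the discordance is again 59–61%. More favourable rates shrink the practical consequence but do not put the margin into the test.

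Fourth, the criterion's words do not mention a confidence bound, and an observed −6.3 points would satisfy them literally. Reading a bound into them is an inference, but the stated one-sided alpha and power only make sense with one.

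**Conclusion.** The concern holds, and the plan must be corrected here. The test called formal does not test the hypothesis for which the trial was designed and sized, and no planned analysis does. At the plan's own design rates, the most likely outcome (59–62%) is a trial that meets the non-inferiority criterion while its formal test is not significant for RTX.

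The sample size is not in error: 63 per arm gives 80.5% power for the margin-based test.

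The figures assume 63 analysed per arm, the design rates, and no adjustment for centre or baseline proteinuria, for which the document gives no planning values. Adjustment would move the power figures somewhat but would not change the null being tested. The 57–58% figure depends on a reading that the plan does not state, and the conclusion does not rest on it.

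**What to change.** 1. In the sample size paragraph, write the null as π_RTX − π_CSA ≤ −0.15. As printed, the difference is set below a positive 15%. This is notation only, since the adjacent wording and the sample size both imply −15 points.
2. In the Statistical and Analytical Plan, replace the formal test with the two-sided 95% confidence interval for the risk difference (RTX minus CSA) in month-24 CR or PR, in all randomised patients under the existing missing-data rule. Conclude non-inferiority if the lower limit is above −15 points.
3. Name one estimator and interval method in advance. One option is the risk difference standardised from the logistic model already planned. With up to 25 sites and 126 patients (126/25, about 5 per site), state how sparse centres are handled. An unadjusted or stratified risk-difference interval is a simpler alternative.
4. Report the same interval, against the same bound, in the per-protocol set as support.
5. Keep the logistic test of OR = 1 as a superiority step, taken only after non-inferiority is met.

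The cost is a change of wording in the statistical section. It needs no additional data or patients, and the total stays at 126.
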